1.0 Objectives

1.1 Describe the purpose, specific aims, or objectives of this research.

Response: The proposed research will translate research on delay discounting to the prevention of Type 2 diabetes (T2D) in persons with prediabetes. In this study, we will test our ability to engage and change the target, delay discounting (DD).

1.2 State the hypotheses to be tested, if applicable.

NOTE: A hypothesis is a specific, testable prediction about what you expect to happen in your study that corresponds with your above listed objectives.

Response: We predict that poverty conditions will increase discounting of the future for ERT subjects, but those receiving EFT will show levels of DD similar to levels observed for participants in the neutral condition. We also predict that EFT will activate brain regions associated with delay of gratification and prospection, and improve executive functions related to EFT, such as working memory.

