2.0 Scientific Endpoints

2.1 Describe the scientific endpoint(s), the main result or occurrence under study.

*NOTE: Scientific endpoints are outcomes defined before the study begins to determine whether the objectives of the study have been met and to draw conclusions from the data. Include primary and secondary endpoints. Some example endpoints are: reduction of symptoms, improvement in quality of life, or survival. Your response should **not** be a date.*

Response: The primary endpoint is the reduction of discounting of the future and increase activation in regions associated with delay of gratification and prospection.

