Participants will be randomly assigned to one of two groups, EFT or ERT, and complete an episodic thinking task. Participants will be randomized by stratifying for education level and sex. The episodic thinking task to generate episodic cues will be similar to the tasks used in our previous studies on EFT's effect (Daniel et al., 2013). Each group will list and describe events for different time periods. The episodic component of the thinking task will occur while the participants are asked to describe what they are imagining about each event (e.g., vacations, weddings, parties, and so forth). EFT participants will list positive future events they are looking forward to and list events that could happen at different general future time points (e.g., 1 month, 2-6 months, 7-12 months). In contrast, the ERT group will list positive recent events (events that have already happened) that they have enjoyed that have occurred at different general time points (e.g., a few hours ago, 1 day ago, 2-6 days ago, 7-12 days ago). All participants will rate the salience, valence, arousal, feasibility and vividness of each event and events with the highest ratings for vividness will be used in the generation of episodic cues. An "imagery" score may be calculated by averaging the frequency/vividness scores for each event. Reductions in rate of discounting occur at higher levels of episodic imagery (Peters & Buchel, 2010). Additionally, participants will record their highest rated events into audio cues.

Participants may also be instructed to use and think about their episodic cues as they engage in a set of executive function tasks (e.g., The Virtual Week) and other decision making tasks such as measures of delay discounting (e.g., discounting of money, food, sedentary behaviors/physical activity, future health; a series of single and cross commodity discounting tasks) and food preferences. Participants will be randomized to which cues (future or recent) they will be instructed to think about when engaging in The Virtual Week task. Executive function tasks may take place on a computer screen or paper and pencil. Participants will complete questionnaires regarding their attention to their episodic cues while engaged in study tasks.

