Adjusting Delay Discounting. The adjusting delay discounting task is a five trial task in which participants are asked how much money they would prefer (e.g. \$500) immediately or a larger reward after a delay (e.g. \$1000). This task is presented on a computer screen and is designed to measure the amount of monetary discounting that occurs when rewards are presented at a delay. This task adjusts the delay to the larger reward and allows for the calculation of k-values. This task will be completed matching each of the traditional tasks parameters (i.e. type and magnitude of the reinforcer).

Executive Function: Cognitive processes, such as planning, cognitive flexibility, working memory, prospective memory, retrospective memory and attention may be measured by using computerized tasks (e.g., with Inquisit) or paper and pencil that involves solving problems, remembering a set of letters or spatial locations while alternating with a distracter tasks, responding to specific stimulus in the presence of an orienting cue, or playing the computer game “The Virtual Week” where users will plan out typical events that could actually happen during the week (e.g., taking their medication, calling their friend, picking up their dry cleaning) (Rendell, & Craik, 2000)

Relative Reinforcing Efficacy Food Purchasing Task: The food purchasing task is modified off of the cigarette purchasing task (CPT) that has been used by Jacobs and Bickel (1999) and assesses a number of different metrics of relative reinforcing efficacy. The procedure we will use is a modified version of this procedure and will assess the relative reinforcing efficacy of a range of foods via

an online survey or computerized task. The chosen food will be displayed during the task so that participants have a frame of reference when completing the questionnaire.

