17.0 Data Management and Analysis

17.1 Describe the data analysis plan, including any statistical procedures. This section applies to both quantitative and qualitative analysis.

Response:

Analytic plan is to use factorial ANCOVA to compare between group differences in different measures of DD, executive function and fMRI-measured brain function for subjects randomly assigned to poverty/neutral conditions and EFT/ERT. Covariates will be used if significant differences between groups are observed in subject characteristics. We predict a main effect of neutral/poverty, such that those assigned to poverty will have higher DD than those assigned to neutral, and an interaction between poverty/neutral and EFT such that in the poverty condition, EFT will reduce the discounting to levels achieved by the wealth, ERT subjects. We also predict when participants who receive EFT under challenge of poverty that EFT will increase activation in brain regions associated with delay of gratification (LPFC and AC) and prospection (hippocampus) relative to those who receive EFT under similar challenges.

17.2 If applicable, provide a power analysis.

NOTE: This may not apply to certain types of studies, including chart/records reviews, survey studies, or observational studies. This question is asked to elicit whether the investigator has an adequate sample size to achieve the study objectives and justify a conclusion.

Response:

The sample size is based on our studies of EFT versus ERT on DD in overweight and obese subjects, which showed an average AUC of $0.54 + 0.28$, and our unpublished research that poverty simulations reduces DD by 34%. We estimate in the ERT condition, neutral simulations will lead to less discounting and higher AUC than poverty simulations (0.54 vs 0.36). We estimate in EFT conditions, that simulations of neutral are associated with a small improvement in discounting in comparison to poverty simulations (0.63 vs 0.54). These predictions suggest that DD in EFT/Poverty and ERT/Wealth will be equivalent. The effect size for this interaction is 0.35. Using the overall SD we observed of 0.28, alpha of .05 and power of 0.80, we can show the effect size for this interaction with 17 Ss/group, or 68 total, or 34 per site in the behavioral portion and in the imaging portion. To be conservative, we will study up to 100 subjects.

17.3 Describe any procedures that will be used for quality control of collected data.

Response:

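### Executive function is a stated hypothesis without endpoint status, a key measure or a multiplicity rule, so a chance result in any one of several optional domains could be reported as confirming it

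*Combined protocol and SAP*

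**What the plan says.** Section 1.2 states a directional hypothesis: EFT will "improve executive functions related to EFT, such as working memory". Section 2.1, under a prompt that asks for primary and secondary endpoints, answers only: "The primary endpoint is the reduction of discounting of the future and increase activation in regions associated with delay of gratification and prospection". Executive function does not appear there, and no secondary endpoint is listed.

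Section 10.3 describes the measurement: "Cognitive processes, such as planning, cognitive flexibility, working memory, prospective memory, retrospective memory and attention may be measured by using computerized tasks". The six domains are given as examples, their measurement is optional, the task types are alternatives joined by *or*, and no score is named. In the behavioral-arm procedures of section 10.1, use of the cues during these tasks is also optional: "Participants may also be instructed to use and think about their episodic cues as they engage in a set of executive function tasks". One task has its own allocation sentence: "Participants will be randomized to which cues (future or recent) they will be instructed to think about when engaging in The Virtual Week task".

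Section 17.1 plans "factorial ANCOVA to compare between group differences in different measures of DD, executive function and fMRI-measured brain function". The specific predictions that follow concern discounting and brain activation only. The sole alpha in the document is in the discounting power calculation of section 17.2: "Using the overall SD we observed of 0.28, alpha of .05 and power of 0.80".

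**The concern.** The plan has a hypothesis and a test for executive function, but no rule for which result would confirm the hypothesis. The domains, the tasks and the scores can all be settled after the data are seen. A chance difference in attention or planning could then be reported as support for a hypothesis fixed in advance, although the only function that hypothesis names is working memory.

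This family of tests is separate from the discounting and activation endpoints. Ordering or adjusting those two would leave the executive-function claim uncontrolled.

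**Working it through.** **The plan's own figure.** The plan states no error rate for executive function. The only result it builds on alpha is the sample size of 17 per group, 68 in total, from section 17.2, where "The effect size for this interaction is 0.35". Take 0.35 as Cohen's f, with an F test on 1 and N − 4 degrees of freedom and noncentrality f²N. Then N = 66 gives power 0.799, N = 67 gives 0.805 and N = 68 gives 0.811. The 68 is reproduced at alpha 0.05. It concerns discounting only. Whether 0.35 is the right value for the interaction is a separate question.

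**Inputs for executive function**
- Number of domains, k: six are named in section 10.3. The list is open and optional, so k = 2 and k = 3 are shown as well.
- Alpha: two-sided 0.05 per test. This is assumed, by carrying over the value given for discounting.
- Contrast: one EFT-versus-ERT test and one score per domain (assumed).
- Correlation between domains, ρ: not given. The range 0 to 0.8 is assumed.

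**Formulas.** For independent domains, the chance of at least one false difference in either direction is 1 − 0.95^k. A false claim of improvement requires the favourable direction, which has probability 0.025 per test, so its chance is 1 − 0.975^k.
- k = 6: 1 − 0.95⁶ = 0.265 and 1 − 0.975⁶ = 0.141.
- k = 3: 1 − 0.95³ = 0.143 and 1 − 0.975³ = 0.073.
- k = 2: 1 − 0.95² = 0.0975 and 1 − 0.975² = 0.049.

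For correlated domains, the same probabilities come from integrating over equicorrelated normal test statistics with cut-off 1.96.

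| Domains tested | ρ | Any false difference | False improvement |
|---|---|---|---|
| 1 | any | 5.0% | 2.5% |
| 2 | 0 | 9.8% | 4.9% |
| 2 | 0.8 | 7.8% | 3.9% |
| 3 | 0 | 14.3% | 7.3% |
| 3 | 0.8 | 9.8% | 4.9% |
| 6 | 0 | 26.5% | 14.1% |
| 6 | 0.5 | 20.7% | 10.4% |
| 6 | 0.8 | 13.9% | 6.9% |

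A simulation of six t-tests with 34 per arm agrees: 21.1% and 10.6% at ρ = 0.5, and 26.4% and 14.0% at ρ = 0.

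**Size of the inflation.** With six domains the false-improvement rate is 6.9/2.5 ≈ 2.8 to 14.1/2.5 ≈ 5.6 times that of a single test. With two domains it is 3.9/2.5 ≈ 1.6 to 4.9/2.5 ≈ 2.0 times. More than one score per task, or accepting either the EFT main effect or the interaction as support, would raise these rates.

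**Check on the remedy.** Testing a key score at 0.05 and, with no gate between them, the other five by Holm does not hold the family at 5%. For independent scores the error is 1 − 0.95 × 0.99⁵ ≈ 9.7%, because Holm's first step is 0.05/5 = 0.01. By simulation it is about 8% at ρ = 0.5 and 6% at ρ = 0.8. Holm must either include the key score or follow its success.

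**The case against.** Executive function is absent from the primary endpoint and from the specific predictions in section 17.1, and section 1.1 names discounting as the target. It is therefore non-primary in effect, and an exploratory label could be all it needs. That stands, and it is why the fix accepts exploratory status for most domains. It does not remove the gap, because section 1.2 states executive function as a prediction and nothing labels it exploratory.

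The number of tests is unknown. The battery may be small, and it may be fixed in the questionnaire attachment cited in section 10.3, which is not part of the document reviewed. This also stands, so the result is conditional and the two- and three-domain figures belong beside it.

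A reader might infer a 21% chance, instead of 5%, of falsely claiming that EFT improves executive function. The documents do not support that. About 21% needs six domains, a correlation near 0.5 and results in both directions, including those where EFT looks worse. For improvement the matching figure is 10.4%, against 2.5%. Nor does the plan say that executive function is tested at an unadjusted 0.05, or that one significant domain is enough. Both are inferred from its silence.

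A reader might also reach about 50% by letting any of the three factorial effects count in each domain. The poverty/neutral main effect does not compare EFT with ERT, so it cannot support a claim about EFT.

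Lastly, The Virtual Week has its own randomization sentence. If that is a second allocation, the EFT-versus-ERT contrast for that task differs from the contrast for the others. The text does not settle this.

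**Conclusion.** The concern holds as a gap in specification with a moderate, conditional effect on the error rate. A stated hypothesis lacks endpoint status, a fixed measure and a rule for confirmation. If all six domains are tested two-sided at 0.05 and any one suffices, the chance of a false difference is about 14% to 26%, and of a false claim of improvement about 7% to 14% against 2.5% for one test. With two or three domains the ranges are about 8% to 14% and 4% to 7%. These figures rest on an assumed correlation of 0.8 to 0, one score per domain and an alpha that the plan sets only for discounting. The primary endpoint is not affected. The correction is a cheap improvement.

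**What to change.** - In sections 2.1 and 17.1, label executive function as secondary.
- Before any comparison by group is seen, name one score on one task as the single key secondary outcome, tested by the EFT-versus-ERT effect at two-sided 0.05. Working memory is the natural candidate because section 1.2 names it, but the choice is the investigators'.
- In section 10.3, commit to measuring that score in every participant of the arm concerned. Report all other domains as exploratory, with estimates and confidence intervals only.
- If claims on other domains are wanted, either apply Holm across all executive-function scores administered, including the key one, or test the others by Holm only after the key score succeeds.
- State that a significant result outside this scheme does not confirm the hypothesis in section 1.2.
- State whether cue allocation for The Virtual Week is the EFT/ERT assignment or a second randomization.

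The cost is wording, with no extra participants or procedures. The other domains lose confirmatory standing, or lose some power under Holm. The plan gives no effect size for executive function, so that loss can only be illustrated. Borrowing the EFT main effect implied by the discounting means in section 17.2 gives f = ((0.63 + 0.54)/2 − (0.54 + 0.36)/2)/2/0.28 = 0.24. Power at Holm's first step over five scores (0.01) would then be about 0.42 instead of 0.66 at N = 100, and 0.26 instead of 0.50 at N = 68.

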11.0 Study Timelines

11.1 Describe the anticipated duration needed to enroll all study subjects.

Response:

This study will complete rolling recruitment and we anticipate it will take approximately 1 year to enroll all study subjects.

11.2 Describe the duration of an individual subject's participation in the study. Include length of study visits, and overall study follow-up time.

Response:

Subjects will attend two appointments, each appointment being approximately 90-120 minutes. This is the same for both arms of the study.

11.3 Describe the estimated duration for the investigators to complete this study (i.e. all data is collected and all analyses have been completed).

Response:

This study will take approximately 2 years to complete.

12.0 Setting

12.1 Describe all facilities/sites where you will be conducting research procedures. Include a description of the security and privacy of the facilities (e.g. locked facility, limited access, privacy barriers). Facility, department, and type of room are relevant. Do not abbreviate facility names.

NOTE: Examples of acceptable response may be: "A classroom setting in the Department of Psychology equipped with a computer with relevant survey administration software," "The angiogram suite at Buffalo General Medical Center, a fully accredited tertiary care institution within New York State with badge access," or, "Community Center meeting hall."

Response:

This research will be conducted at the University at Buffalo (UB) and Virginia Polytechnic Institute and State University (VT) as well as their corresponding fMRI facilities. All facilities are locked and require key or badge access to enter in relevant research areas.

The UB team will conduct research at the Division of Behavioral Medicine Research Labs, located in G56, G58, G90 and 151 Farber Hall, University at Buffalo South Campus. The fMRI scans will be conducted at local fMRI facilities located at Dent Neurologic Institute ([name]).

The VT research team will conduct research at the Virginia Tech Carilion Research Institute, in Roanoke and Blacksburg locations. The fMRI scans will also be conducted at the Virginia Tech Carilion Research Institute, also in Roanoke or Blacksburg. Recruitment and screening will be in collaboration with Carilion Clinic Department of Family and Community Medicine in Roanoke and surrounding areas.

12.2 For research conducted outside of UB and its affiliates, describe:

- Site-specific regulations or customs affecting the research
- Local scientific and ethical review structure

NOTE: This question is referring to UB affiliated research taking place outside UB, i.e. research conducted in the community, school-based research, international research, etc. It is not referring to multi-site research. UB affiliated institutions include Kaleida Health, ECMC, and Roswell Park Cancer Institute.

Response:

Dent Neurologic Institute will follow the same scientific and ethical review structure as the University at Buffalo. All research staff working on the project will need to complete Human Subjects Training as per the University requirements. Staff will be trained across sites to follow the same procedures and weekly/monthly meetings will be organized to ensure this.

N/A: This study is not conducted outside of UB or its affiliates.

13.0 Community-Based Participatory Research

13.1 Describe involvement of the community in the design and conduct of the research.

NOTE: Community-Based Participatory Research (CBPR) is a collaborative approach to research that equitably involves all partners in the research process and recognizes the unique strengths that each brings. CBPR begins with a research topic of importance to the community, has the aim of combining knowledge with action and achieving social change to improve health outcomes and eliminate health disparities.

Response:

N/A: This study does not utilize CBPR.

13.2 Describe the composition and involvement of a community advisory board.

Response:

- N/A: This study does not have a community advisory board.

14.0 Resources and Qualifications

14.1 Describe the qualifications (e.g., education, training, experience, expertise, or certifications) of the Principal Investigator **and** staff to perform the research. When applicable describe their knowledge of the local study sites, culture, and society. Provide enough information to convince the IRB that you have qualified staff for the proposed research.

NOTE: If you specify a person by name, a change to that person will require prior approval by the IRB. If you specify a person by role (e.g., coordinator, research assistant, co-investigator, or pharmacist), a change to that person will not usually require prior approval by the IRB, provided that the person meets the qualifications described to fulfill their roles.

Response:

The Principal Investigator, [name] is a Distinguished Professor of Pediatrics, and Social and Preventive Medicine at the State University of New York at Buffalo. [name] has published over 300 papers in peer reviewed journals. The project coordinator and research staff have experience in behavioral research using similar methodology and have completed the appropriate certifications: CITI and CPR/First Aid/AED.

Describe other resources available to conduct the research.

14.2 Describe the time and effort that the Principal Investigator and research staff will devote to conducting and completing the research.

NOTE: Examples include the percentage of Full Time Equivalent (FTE), hours per week. The question will elicit whether there are appropriate resources to conduct the research.

Response:

The Principle Investigator will devote approximately 8-10 hours per week to meet with staff, oversee data safety and discuss recruitment and study specific information.

The Project Coordinator will spend approximately 40% of their time training and supervising staff, including conducting weekly project meetings, 10% completing the Human Subjects Review Process, 20% coordinating the scheduling of appointments for staff and prospective subjects, 10% coordinating and assisting in the test sessions, 10% coordinating multisite weekly meetings, and 10% overseeing the development of study materials.

Research Assistants will spend approximately 50% of their time training and running participants, 20% recruiting subjects, 20% developing project materials,

including questionnaires, surveys, and forms, and 10% entering data and quality control of the data collected during the study

14.3 Describe the availability of medical or psychological resources that subjects might need as a result of anticipated consequences of the human research, if applicable.

NOTE: One example includes: on-call availability of a counselor or psychologist for a study that screens subjects for depression.

Response:

The availability of experienced endocrinologists will be available for our study that examines subjects at risk for Type 2 Diabetes.

If a participant scores high on the PHQ-9 (greater than or equal to 10) or they respond with any answer other than “not at all” to the suicidality question, the project coordinator and PI will be notified. These participants will also be provided with a resource list (see supporting document “Resource List” with name, address, and phone number of local and national counseling resources, crisis services, and emergency services.

During any of the visits, if the participant appears to extremely upset (e.g. emotional, crying,) the project coordinator and PI will be notified. These participants will be asked to fill out the Beck Depression Inventory as well as provided with the list of resources. We will notify this participant’s physician of their depression score by mail, fax, or phone call, and suggest that they follow up with their patient. Additionally, we will follow up with the participant within the next 24 hours.

14.4 Describe your process to ensure that all persons assisting with the research are adequately informed about the protocol, the research procedures, and their duties and functions.

Response:

All personnel working on the project are required to complete the CITI training as required by IRB. Additionally, there are extensive procedures manuals that are read and followed by all personnel. The Project Coordinator is responsible for training staff on data collection and recording procedures.

Project coordinator and the principal investigators will be responsible for ensuring proper staff training on study procedures and consistency of data collection between each site. This will be achieved through local training, regular communication between sites and coordinating procedural materials for experimenters.

